7.4.4. Derivation of Patient-Reported Outcome

7.4.4.1. Numerical Rating Scale Score for Pain Associated with Uterine Fibroids

Patients completed daily eDiaries including assessment of uterine fibroid-associated pain by the Numerical Rating Scale (NRS). Patients rated their worst pain in the last 24 hours caused by their uterine fibroids on a scale from 0 to 10, with 0 indicating no pain and 10 indicating pain as bad as you can imagine. The maximum NRS score for pain at Week 24/EOT is calculated as the maximum NRS score during the last 35 days on study treatment. If any NRS scores for pain during the last 35 days on study treatment are missing, the maximum score will be calculated as the maximum of all non-missing scores. Baseline NRS score for uterine fibroid-associated pain is defined as the maximum NRS score from the 35 days of data collected prior to randomization.

Proportion of women who achieve a *maximum* NRS score for pain associated with uterine fibroids over the last 35 days of treatment that is at least a 30% reduction from Baseline will be summarized in the subset of women with a maximum pain score ≥ 4 during the 35 days prior to randomization (subset). In addition, for the subset, mean maximum NRS scores will be provided by treatment and visit. Maximum NRS score for each patient at a visit is defined as the highest NRS score reported in the visit window specified in [Table 2](#).

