For key secondary endpoint 4, an increase in hemoglobin of 2g/dL is considered clinically meaningful, because it corresponds to approximately the same increase as that expected after a transfusion of ~ 2 units of packed red blood cells (Man, 2016; Bachowski, 2017).

For deriving the key secondary endpoint 5 (proportion of women who achieve a maximum NRS score ≤ 1 for uterine fibroid-associated pain over the last 35 days of treatment in the subset of women with a maximum pain score ≥ 4 during the 35 days prior to randomization), the patient subset and Week 24/EOT maximum value are determined as follows.

Because patients were asked to begin eDiary entries after returning the first collection of feminine products, the number of eDiary entries made during screening varies with the duration of screening for each patient. Some patients required only one collection to be randomized, whereas others required as many as four collections to confirm eligibility.

Once the qualifying menstruation was completed and the patient qualified for randomization based upon resulting MBL volume(s), the recording of patient's NRS scores for screening phase will be ended and the number of pain score days at Baseline can be as short as 7 days or as long as 70 days prior to randomization. If a patient meets the subset definition (maximum NRS score ≥ 4 at Baseline) over a portion of the screening days (eg, 7-70 days), she will also meet the subset definition on the entire 35 days interval.

Since the maximum NRS value is used to determine inclusion into the subset rather than an average NRS value, the variable number of days for inclusion of patients has no major impact on determining patient subset. To ensure robust estimate of response, the minimum number of non-missing daily pain scores required to calculate the maximum score at Week 24/EOT is at least 28 days (80% of the last 35 days of treatment) of pain scores recorded in the e-Diary entry.

The primary analysis of key secondary endpoint 5 will be analyzed for the subset of women who have a maximum pain score ≥ 4 during the 35 days prior to randomization and who have at least 28 days (80% of the last 35 days of treatment) of pain scores recorded in the e-Diary at Week 24/EOT. In addition, a sensitivity analysis will be conducted on the subset of women who have

Statistical Analysis Plan
Amendment 1: Effective June 14, 2019

MVT-601-3001 and 3002

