a maximum pain score ≥ 4 during the 35 days prior to randomization without restricting number of days of pain scores recorded in the e-Diary.

The analysis for endpoint 5 (proportion of women who achieve a maximum NRS score ≤ 1 for uterine fibroid-associated pain over the last 35 days of treatment in the subset of women with a maximum pain score ≥ 4 during the 35 days prior to randomization) will also be performed using NRS scores reported on eDiary during menstrual and non-menstrual days.

For key secondary efficacy endpoints (6 and 7) evaluating percent change from Baseline in uterine fibroid volume and uterine volume that are measured only at Week 24, an analysis of covariance (ANCOVA) model will be used to assess treatment effect with treatment, randomization stratification factors and Baseline value as covariates.

For key secondary efficacy endpoints (2 and 3) evaluating the change (absolute or % change) from Baseline to Week 24, treatment comparisons will be performed using a mixed model repeated measures approach with treatment, visit, randomization stratification factors and treatment by visit interactions included as fixed effects and random effects (from the individual patients). In this model, an unstructured variance-covariance matrix is assumed for each patient.

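### The 30% pain-reduction endpoint sets no minimum number of diary days for the Week 24/EOT maximum NRS, so sparse on-treatment diaries lean toward response

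*SAP*

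**What the plan says.** **Section 7.4.4.1.** The maximum NRS at Week 24/EOT is "calculated as the maximum NRS score during the last 35 days on study treatment". If some days are missing, "the maximum score will be calculated as the maximum of all non-missing scores". No minimum number of days is given. The same section defines the 30% endpoint as the proportion with a maximum score "over the last 35 days of treatment that is at least a 30% reduction from Baseline will be summarized in the subset" whose Baseline maximum was at least 4. Appendix 1 tests this endpoint with a Cochran-Mantel-Haenszel test at P < 0.05. Table 1 lists it under other secondary endpoints, outside the testing hierarchy.

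**Section 7.4.1.** In a passage that opens "For deriving the key secondary endpoint 5", the SAP says that "the minimum number of non-missing daily pain scores required to calculate the maximum score at Week 24/EOT is at least 28 days", and gives this as 80% of 35. The main analysis of endpoint 5 is limited to women who meet it. A sensitivity analysis of endpoint 5 is planned "without restricting number of days of pain scores recorded in the e-Diary". The section also notes that the "number of pain score days at Baseline can be as short as 7 days or as long as 70 days prior to randomization".

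**By-visit summaries.** "Maximum NRS score for each patient at a visit is defined as the highest NRS score reported in the visit window" of Table 2. Appendix 1 lists the mean maximum over time as descriptive.

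The amended SAP and the pre-amendment SAP in the same file carry the same wording on all of this.

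**The concern.** A same-named quantity, the Week 24/EOT maximum NRS, has a completeness requirement for one endpoint and none for another. The SAP justifies the 28 days as needed for a robust estimate of response. That reason applies equally to a 30% reduction in the same maximum.

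The direction of the error is known. Deleting days from a set of scores cannot raise its maximum. Footnote b to Table 1 says fibroid pain occurs mostly on menstrual days and that 35-day mean scores are below 1 for most patients. A short diary can therefore easily contain only pain-free days, and the woman then counts as a responder with no change in her pain. If diary completion on treatment differs between arms, the comparison is biased.

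Other endpoints in the SAP have a guard. Table 7 counts under 4 weeks of exposure as non-response, and the spotting and amenorrhea rules that rely on the eDiary need an entry rate above 70%. The 30% endpoint has no such guard.

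A lesser matter is that a maximum also depends on how many days it is taken over, and the Table 2 windows are not of equal length.

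**Working it through.** **1. The SAP's own figure.** 28/35 = 0.80, which agrees with the stated 80%.

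**2. Chance of missing every painful day.** Let k of the 35 days be painful and n days be recorded, with recorded days a random subset. Then

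P(no painful day recorded) = C(35 − k, n) / C(35, n).

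The SAP gives no value for k. I assume k = 5 and show 3 to 7 as a range. Worked case, k = 5 and n = 3: C(30,3)/C(35,3) = 4060/6545 = 0.620.

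| Recorded days n | k = 3 | k = 5 | k = 7 |
|---|---|---|---|
| 3 | 76% | 62% | 50% |
| 7 | 50% | 30% | 18% |
| 14 | 20% | 6.3% | 1.7% |
| 21 | 5.6% | 0.6% | 0.05% |
| 28 | 0.5% | 0.006% | < 0.001% |

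The 28-day minimum almost removes the problem when days are missing at random.

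**3. Missing as a block.** Suppose instead that the last 7 of the 35 days are missing and a k-day episode is equally likely to start on any of 35 − k + 1 days. It is missed if it starts on Day 29 or later. For k = 5 this is 3/31 = 10%; for k = 3, 5/33 = 15%; for k = 7, 1/29 = 3%. The 28-day rule leaves some residual error in this case.

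**4. Illustrative 30% response with no true change.** Simulation assumptions: 28-day cycle, 5 pain days, pain-day scores about N(5, 2) rounded and clipped to 0–10, other days 0, a complete 35-day Baseline diary, Baseline maximum at least 4, on-treatment days missing at random. Response means maximum ≤ 0.7 × Baseline maximum.

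| Recorded days | Apparent response |
|---|---|
| 3 | 78% |
| 7 | 55% |
| 14 | 32% |
| 21 | 19% |
| 28 | 12% |
| 35 | 9% |

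The 9% with complete diaries is chance variation, so only the excess over 9% is due to missing days: 3 points at 28 days, 23 at 14, 46 at 7 and 69 at 3.

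**5. By-visit windows.** Length = End Day − Start Day + 1, from Table 2.

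- Week 4: 43 − 1 + 1 = 43 days.
- Week 8: 71 − 44 + 1 = 28 days; Weeks 12, 16 and 20 likewise.
- Week 24: 196 − 156 + 1 = 41 days nominally. Treatment lasts 24 weeks (168 days) and the target visit is Day 169, so a woman finishing on schedule has 168 − 156 + 1 = 13 or 169 − 156 + 1 = 14 on-treatment days in it.

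Under the pain pattern of step 4, unchanged over time, the mean maximum is 7.7 over 43 days, 7.65 over 41, 7.3 over 28 and 4.4 over 14. Much of the last drop arises because a 14-day window meets a 5-day episode in a 28-day cycle only (14 + 5 − 1)/28 = 64% of the time.

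**The case against.** **The sections can be reconciled.** A reader might infer that 7.4.4.1 contradicts 7.4.1. The documents do not support that. The 28-day rule is introduced for endpoint 5 and then restated as a limit on who enters its main analysis, while 7.4.4.1 says how a maximum is formed when days are missing. This objection stands. What remains is that the 30% endpoint has no minimum.

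**Early stopping.** A reader might infer that early discontinuation in general manufactures responders. It does not. The interval is anchored to the last 35 days on treatment, so a woman stopping at Week 12 or Week 20 still has a full look-back. Only stopping before about Day 35 shortens it.

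**The Week 24 curve.** A reader might infer from the nominal 41 days that the curve is raised at Week 24. For a woman finishing on schedule the window holds about 13–14 on-treatment days, so the likely distortion is downward. The Week 4 effect is small: 7.70 − 7.31 = about 0.4 points in the illustration.

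**Baseline works the other way.** Baseline diaries can be as short as 7 days. That lowers the Baseline maximum and works against response. True, but those days precede randomization, whereas on-treatment missingness can differ by arm, so the two need not cancel.

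**Size and weight.** The pain pattern is assumed, the large errors need very sparse diaries, and the SAP does not say how many women have them. The endpoint carries a nominal p-value and the by-visit curve is descriptive. All of this stands and limits the point's weight. It does not alter the direction of the bias.

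**The endpoint 5 sensitivity analysis.** Applying the 30% rule there would be wrong. It exists to show what happens without the day restriction, and its criterion is a maximum of 1 or less.

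**Conclusion.** The concern holds in a limited form. As written, the 30% endpoint accepts any number of diary days, and the resulting error favors response. The direction follows from the definition of a maximum and from the SAP's own statement about when pain occurs.

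The size depends on assumed inputs. With 5 painful days in 35 and random missingness, the chance of missing them all is 62% at 3 entries, 30% at 7, 6% at 14 and under 0.01% at 28. With 3 to 7 painful days it is 76% to 50% at 3 entries and 50% to 18% at 7. The effect on the arm comparison cannot be computed, because the frequency of sparse diaries and any imbalance between arms are not given.

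The alpha-protected pain endpoint already has the 28-day safeguard in its main analysis, so this is a worthwhile, inexpensive improvement to a nominally tested secondary endpoint. The window lengths are a secondary, descriptive matter: with unchanged pain the curve may sit slightly high at Week 4 and low at Week 24.

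**What to change.** In Section 7.4.4.1, for the 30% endpoint only, state in this order:

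1. Any recorded score above 70% of the Baseline maximum in the last 35 days on treatment is failure, whatever the number of entries.
2. Otherwise, response requires at least 28 recorded days in that interval.
3. Otherwise, the woman counts as a non-responder.

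This applies the SAP's own completeness standard and discards no evidence of failure. Leave the unrestricted sensitivity analysis of endpoint 5 as planned.

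For the by-visit maxima, replace the Table 2 windows with equal 28-day look-backs ending at each visit and limited to on-treatment days.

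The cost is SAP wording and derivation code. The downside is that some women with sparse diaries move from responder to non-responder, including some whose pain did improve. Counting sparse diaries as non-response is one choice among several, so report the number of women affected by arm.

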7.4.4.2. UFS-QoL Score

Calculation of UFS-QoL Symptom Severity Scale Score

To calculate the Symptom Severity Scale score, a summed score is created for the items listed below and then the formula below the table is used to transform raw scores to a normalized score with a range of possible values from 0 to 100. This provides Symptom Severity Scale scores, where higher scores are indicative of greater symptom severity and lower scores indicate lower symptom severity.

Scale	Sum Item Values	Lowest and Highest Possible Raw Scores	Possible Raw Score Range
Symptom Severity	Sum 1 – 8	8, 40	32

Formula for Transformation of Symptom Severity Raw Scores ONLY:

$$\text{Transformed Score} = [(\text{Actual raw score} - \text{lowest possible raw score}) / (\text{Possible raw score range})] * 100$$

Calculation of UFS-QoL Bleeding and Pelvic Discomfort Scale Score

The UFS-QoL Bleeding and Pelvic Discomfort (BPD) Scale has been derived from the UFS-QoL Symptoms Scale; the derivation and validation of this new scale can be found in [Appendix 3](#). The new scale consists of the following three symptoms proximal to uterine fibroids:

- Heavy bleeding during your menstrual period (Q1)
- Passing blood clots during your menstrual period (Q2)
- Feeling tightness or pressure in your pelvic area (Q5)

To calculate the score for the BPD Scale, a summed score of the items listed below is created and then the formula below the table is used to transform the raw score to a normalized score. This provides BPD Scale scores, where higher score values are indicative of greater symptom severity and lower scores will indicate minimal symptom severity (high scores = bad).

Sub-Scale	Sum Item Values	Lowest and Highest Possible Raw Scores	Possible Raw Score Range
Q1, Q2 and Q5	Sum 1,2,5	3, 15	12

Formula for Transformation of BPD Raw Scores ONLY:

$$\text{Transformed Score} = [(\text{Actual raw score} - \text{lowest possible raw score}) / (\text{Possible raw score range})] * 100$$

On the basis of transformed score for BPD Scale, change from Baseline in the transformed score for BPD Scale at Week 24 will be defined as an alpha-protected key secondary endpoint comparing the relugolix + E2/NETA group with the placebo group. The proportion of patients who are responders (defined as meeting a meaningful change threshold from Baseline in the BPD Scale) at Week 24 on the transformed score for the BPD Scale will be compared between the two treatment arms (the relugolix + E2/NETA group with the placebo group) using a stratified Cochran-Mantel-Haenszel test, as appropriate. The proposed responder threshold is a 20-point change. Details in the determination of the meaningful change in the BPD Scale can be found in [Appendix 4](#).

As a descriptive assessment on robustness of the responder analysis, a plot of the cumulative distribution function (CDF) will be provided for each treatment group to display the change from Baseline to Week 24 in the transformed score for BPD Scale on the x-axis and cumulative percentage of patients experiencing up to that change on the y-axis.

Calculation of Other UFS-QoL Scale Scores and UFS-QoL Total Score

For the other UFS-QoL scales (concern, activities, revised activities, energy/mood, control, self-conscious, and sexual function), a summed score of the items listed below is created for each individual scale. To calculate the UFS-QoL total score, the values for each individual scale are summed. Using the formula below the table, all raw scores are transformed to normalized scores. Higher scores are indicative of better health-related quality of life (high = good).

For endpoints evaluating a single question, the raw score is used in the analysis. The activity and revised activity domain scores will be summarized by treatment group.

Scale	Sum Item Values	Lowest and Highest Possible Raw Scores	Possible Raw Score Range
Concern	9+15+22+28+32	5, 25	20
Activities	10+11+13+19+20+27+29	7, 35	28
Revised activities	11+13+19+20+27	5,25	20
Energy/mood	12+17+23+24+25+31+35	7, 35	28
Control	14+16+26+30+34	5, 25	20
Self-conscious	18+21+33	3, 15	12
Sexual function	36+37	2, 10	8
HRQL TOTAL	Sum of 6 Subscale Scores ^a	29, 145	116

Abbreviations: HRQL, health-related quality of life.

^a HRQL Total includes following scales: concern, activities, energy/mood, control, self-conscious, and sexual function.

Formula for Transformation of Raw Scores of Other Scale Scores ONLY:

$$\text{Transformed Score} = [(\text{Highest possible score} - \text{Actual raw score}) / (\text{Possible raw score range})] * 100$$

For revised activities, the proportion of patients who are responders (defined as meeting a meaningful change from Baseline in the revised activity score) at Week 24 will be analyzed similarly to that for the change in BPD Scale score between the two treatment arms (relugolix + E2/NETA and placebo). The proposed responder threshold is a 20-point increase. Details of the determination of the meaningful change in the Revised Activities Scale score can be found in [Appendix 5](#).

Missing Items

For any scale analyses, if < 50% of the scale items are missing, the scale should be retained using the mean scale score of the items present. If ≥ 50% of the items are missing, no scale score should be calculated; the subscale score will be considered missing.

7.4.4.3. Patient Global Assessment

The PGA for function and symptoms will be evaluated using a 5-point response scale (eg, absent, mild, moderate, severe, and very severe). To calculate change from Baseline to Week 24, the following numerical scores will be assigned to each response level:

Response Scale (Function)	Response Scale (Symptoms)	Numerical Score
No limitation at all	Not severe	1
Mild limitation	Mildly severe	2
Moderate limitation	Moderately severe	3
Quite a bit of limitation	Very severe	4
Extreme limitation	Extremely severe	5

Statistical Analysis Plan
Amendment 1: Effective June 14, 2019

MVT-601-3001 and 3002

For each item, the count and proportion of improvement by level or at least one level will be tabulated by treatment group and by visit. The denominator for the proportion will be based on the number of patients who provided non-missing responses to the items.

7.4.4.4. Menorrhagia Impact Questionnaire

The Menorrhagia Impact Questionnaire items 3 and 4 will be evaluated using the 5-point response scales (Not at all, Slightly, Moderately, Quite a bit, and Extremely) to assess level of improvement from Baseline to Week 24.

For each item, the count and proportion of improvement by level will be tabulated by treatment group and by visit. The denominator for the proportion will be based on the number of patients who provided non-missing responses to the items.

7.5. Exploratory Efficacy Endpoints

The following exploratory endpoints will be assessed for both comparisons the relugolix + E2/NETA group with the placebo group and the relugolix + delayed E2/NETA group with the placebo group:

- Change from Baseline to Week 24 in the EQ-5D-5L Scale score
- Change from Baseline to Week 24 in EQ-5D-5L visual analogue score.

7.5.1. Exploratory Efficacy Analyses

Analysis methods previously described for primary and secondary efficacy endpoint analyses will be used for the analysis of these endpoints.

8. PHARMACOKINETIC AND PHARMACODYNAMIC ANALYSES

Plasma relugolix, plasma NET, and serum E2 trough concentrations will be listed and summarized by study, treatment group (Group A, B, or C), and visit.

Serum pharmacodynamic data (LH, FSH, E2, and progesterone) will be listed and summarized using descriptive statistics (including raw and change from Baseline) by study, treatment group (Group A, B, or C), and visit.

For pharmacodynamic assessment, the number and percentage of patients with individual E2 concentration values < 10 pg/mL, 10 to < 20 pg/mL, 20 to < 50 pg/mL, and \geq 50 pg/mL and individual progesterone concentration values < 1 ng/mL, 1 to 5 ng/mL, and \geq 5 ng/mL will be summarized by treatment group (Group A, B, or C) and visit.

Scatter plots with LOESS smoothing lines for MVT-601-3001 and MVT-601-3002 separately will be used to examine the relationship between mean plasma relugolix trough concentration at the given time point (collected between 18 and 30 hours after the previous dose) and the following pharmacodynamic concentrations:

- Week 12 serum LH, FSH, E2, and progesterone (separately for Groups A and B);
- Week 24 serum LH, FSH, E2, and progesterone (separately for Groups A and B, and Groups A and B combined).

In addition, the PK data from this study will be combined with PK data from other studies to define a population PK model, which will be reported separately. Exposure-response analyses of the primary efficacy endpoint and safety will be conducted to assess the effect of relugolix exposure on outcomes. The analysis plan for population PK and exposure-response analyses will be specified in a separate document.

9. SAFETY ANALYSES

Unless otherwise specified, safety analyses will be conducted using the safety population according to the treatment received by the patients.

9.1. Adverse Events

Adverse events will be collected from the time of the first dose of study drug through the safety follow up visit approximately 30 days after the last dose of study drug (the end of treatment period), or the date of initiation of another investigational agent or hormonal therapy or surgical intervention or entering extension study, whichever occurs first. Serious adverse events reported to the investigator after the safety reporting period should be reported to the sponsor if the investigator assesses the event as related to study drug.

The severity of all treatment-emergent adverse events will be evaluated by the investigator based on the National Cancer Institute's Common Terminology Criteria for Adverse Events (CTCAE) and will be coded to preferred term and system organ class using MedDRA 22.0 or higher.

A treatment-emergent adverse event is defined as any adverse event that occurs after administration of the first dose of study drug.

Adverse event summaries will be based on treatment-emergent adverse events, unless otherwise specified. Adverse events occurring prior to administration of any study drug will be listed and flagged in by-patient listings.

The following tabular summaries that include the number and percentage of patients will be provided:

- Overview of adverse events;
- All adverse events;
 - By SOC and PT;
 - By decreasing frequency of PT;
 - By SOC, PT, and maximum severity;
 - Study drug-related per investigator by SOC and PT;
 - By time to onset, SOC and PT;
- Grade 3 or above adverse events;
 - By SOC and PT;
 - By decreasing frequency of PT;
 - Study drug-related per investigator by SOC and PT;
- Grade 2 or above adverse events;
 - By SOC and PT;
 - By decreasing frequency of PT;
 - By SOC, PT, and maximum severity;

- Study drug-related per investigator by SOC and PT;
- Adverse events leading to study drug withdrawal;
 - By SOC and PT;
 - By decreasing frequency of PT;
- Adverse events leading to dose interruption;
 - By SOC and PT;
 - By decreasing frequency of PT;
- Adverse events resulting in fatal outcome;
 - By decreasing frequency of PT;
- Serious adverse events;
 - By SOC and PT;
 - By decreasing frequency of PT;
 - By SOC, PT, and maximum severity;
 - By SOC, PT, and relationship to study drug;
- Adverse events of clinical interest (ALT or AST $\geq 3 \times$ ULN);
 - By SOC, PT, and maximum severity;
 - By decreasing frequency of PT.

Additionally, adverse event categories defined in [Table 12](#) will be summarized by decreasing frequency of PT.

